### 7.2.3 Visit 3/ED ~5 (4 ED ±1)

At Visit 3, the following assessments and procedures will be performed as displayed in Section 1.3.2.

- Height/length and weight
- Vital signs (see Section 8.2 for details)
- Concomitant medication review
- Review of EPD entries and bleeding history
- Blood sampling for laboratory tests
  - FVIII inhibitor assessment (Section 8.10)
  - FVIII:C trough level ( $\geq$ 48 hours after the last FVIII treatment)
- AE review
- Study drug dispensation for home infusions in accordance with the IxRS drug dispensing schedule
- Return used and unused study intervention (study drug accountability)
- Continue regular biweekly contact between the participant's parent/caregiver and the site to check EPD documentation and AE review until the End of Study/Early Termination

#### 7.2.4 Visit 4/ED ~10 (9 ED ±1)

At Visit 4, the following assessments and procedures will be performed as displayed in Section 1.3.2.

- Height/length and weight
- Vital signs (see Section 8.2 for details)
- Concomitant medication review
- Review of EPD entries and bleeding history
- Blood sampling for laboratory tests
  - FVIII inhibitor assessment (Section 8.10)
  - FVIII:C trough level ( $\geq 48$  hours after the last FVIII treatment)
- AE review
- Study drug dispensation for home infusions in accordance with the IxRS drug dispensing schedule
- Return used and unused study intervention (study drug accountability)
- Continue regular biweekly contact between the participant's parent/caregiver and the site to check EPD documentation and AE review until the End of Study/Early Termination

#### 7.2.5 Visit 5/ED ~15 (14 ED ±1)

At Visit 5, the following assessments and procedures will be performed as displayed in Section 1.3.2.

- Height/length and weight
- Vital signs (see Section 8.2 for details)
- Concomitant medication review
- Review of EPD entries and bleeding history
- Blood sampling for laboratory tests
  - FVIII inhibitor assessment (Section 8.10)
  - FVIII:C trough level ( $\geq 48$  hours after the last FVIII treatment)
- AE review
- Study drug dispensation for home infusions in accordance with the IxRS drug dispensing schedule
- Return used and unused study intervention (study drug accountability)
- Continue regular biweekly contact between the participant's parent/caregiver and the site to check EPD documentation and AE review until the End of Study/Early Termination

#### 7.2.6 Visit 6/ED 20 (20 ED ±1)

At Visit 6, the following assessments and procedures will be performed as displayed in Section 1.3.2.

- Height/length and weight
- Vital signs (see Section 8.2 for details)

- Concomitant medication review
- Review of EPD entries and bleeding history
- Blood sampling for laboratory tests
  - FVIII inhibitor assessment (Section 8.10)
  - FVIII:C trough level ( $\geq$ 48 hours after the last FVIII treatment)
- In-hospital administration of study intervention
- Blood sampling after administration of study intervention (Section 7.3.2):
  - Incremental recovery (15 to 30 minutes post infusion)
- AE review
- Study drug dispensation for home infusions in accordance with the IxRS drug dispensing schedule
- Return used and unused study intervention (study drug accountability)
- Continue regular biweekly contact between the participant's parent/caregiver and the site to check EPD documentation and AE review until the End of Study/Early Termination

### 7.2.7 Visit 7/Interim Visit/30 to 40 ED

This visit is required only for PUPs and MTPs who have less than 40 ED 6 months after the Baseline visit. The intent is to have at least one scheduled visit between completion of 20 ED and the expected date of accumulating 50 ED. The primary purpose of the visit is to assess the well-being of the participant, ensure continued compliance with the treatment, and make any needed adjustments in dosage or infusion frequency based upon weight or bleeding events.

The following procedures and assessments will be performed:

- Height/length and weight
- Vital signs (see Section 8.2 for details)
- Concomitant medication review
- Review of EPD entries and bleeding history
- Blood sampling for laboratory tests
  - FVIII inhibitor assessment (Section 8.10)
  - FVIII:C trough level ( $\geq$ 48 hours after the last FVIII treatment)
- AE review
- Study drug dispensation for home infusions in accordance with the IxRS drug dispensing schedule
- Return used and unused study intervention (study drug accountability)
- Continue regular biweekly contact between the participant's parent/caregiver and the site to check EPD documentation and AE review until the End of Study/Early Termination

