Abbreviations: ED = exposure days; EPD = electronic patient diary; FVIII = factor VIII; ITI = immune tolerance induction; MTP = minimally treated patients; PUP = previously untreated patients; RAVE = data base for electronic case report

- a The scheduled study visits are shown in the table. Unscheduled visits are permitted at any time at the discretion of the investigator.
- b For MTPs, the Screening visit should only take place after a washout period of at least 72 hours following any previous treatment with any FVIII replacement product.
- c This visit is required only for PUPs and MTPs who have less than 40 ED, 6 months after the Baseline visit. The intent is to have at least one scheduled visit between completion of 20 ED and the expected date of accumulating 50 ED. The primary purpose of the visit is to assess the well-being of the participant, ensure continued compliance with the treatment, and make any needed adjustments in dosage or infusion frequency based upon weight or bleeding events.
- d For participants who do not develop high-titer FVIII inhibitor, the Final visit can be performed as soon as a minimum of 50 ED is achieved, but no later than 2 weeks after achieving 50 ED.
- e This follow-up is not required for study participants who develop high-titer inhibitor and continue in the study in the Optional ITI Treatment (Section 10.5.1).
- f Height/length and weight will be obtained for all participants at screening and at all subsequent visits.
- g Prior medications will be recorded at screening as part of medical history. Concomitant medications will be recorded at subsequent visits.
- h Inhibitor is to be evaluated at screening and in repeat sampling at least 1 week but not more than 2 weeks after screening (local laboratory testing) in MTPs only (i.e., unnecessary to be evaluated in PUPs). For MTPs, FVIII level and presence of FVIII inhibitor should be measured at least 72 hours after the last dose of FVIII. For MTPs, study drug administration should start upon availability of result from local laboratory testing documenting negative inhibitor titer.
- i Baseline inhibitor testing will be done in MTPs only.

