#### 4.1.2 Part B (PUPs/MTPs)

Part B will assess the efficacy and safety of KOVALTRY in previously untreated/minimally treated Chinese children with severe hemophilia A. Part B will investigate approximately 6 PUPs/MTPs. Efficacy and safety assessments are outlined in the SoA in Section 1.3.2.

Efficacy and safety data for the use of KOVALTRY for treatment of bleeding episodes will also be collected.

- Study participants will be treated until at least 50 ED is achieved.
  - Treatment may begin with start of prophylaxis with 15 to 50 IU/kg (minimum dose: 250 IU) at least 1 day a week; alternatively, prophylaxis

can be started directly with a once-a-week schedule minimum dose of 250 IU for PUPs/MTPs of any weight.

- The starting dose may be tailored to the participant's weight or demonstrated bleeding tendency.
- Individual participant dose decisions are at the discretion of the investigator.
- Part B will include 8 study visits (Screening, Baseline, Visit 3 [approximately 5 ED], Visit 4 [approximately 10 ED], Visit 5 [approximately 15 ED], Visit 6 [approximately 20 ED], Visit 7/Interim visit [approximately 30 to 40 ED], and Visit 8/Final visit [50 ED]/Early Termination). All parents/caregivers of participants in Part B will receive a safety follow-up call approximately 2 weeks after the end of treatment.

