### **8.10.2 Part B (PUPs/MTPs) Immunogenicity Assessments**

In Part B, the requirement for FVIII inhibitor testing before start of study treatment at Screening and Baseline will only be done in MTPs; this assessment is not applicable for PUPs. The absence of inhibitors will be assessed by local laboratory testing at Screening ( $< 0.6$  BU/mL) of 2 consecutive samples at least 1 week but not more than 2 weeks apart.

After study treatment is started, PUPs/MTPs must be tested for development of inhibitor to study drug (KOVALTRY) at Visit 3 [approximately 5 ED], Visit 4 [approximately 10 ED], Visit 5 [approximately 15 ED], Visit 6 [approximately 20 ED], Visit 7/Interim visit [approximately 30 to 40 ED], and Visit 8/Final visit [50 ED]/Early Termination). The first positive inhibitor test must be confirmed by analysis of a second sample and by analysis of FVIII level recovery within 2 weeks of notification. After confirmation of the positive result, the inhibitor development will be reported as SAE.

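### Part B: requiring Visit 7 only for children with fewer than 40 ED at 6 months leaves faster-accruing children with no scheduled inhibitor test from about ED 20 to ED 50

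*Protocol*

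**What the plan says.** Protocol 7.2.7 sets the condition: "This visit is required only for PUPs and MTPs who have less than 40 ED 6 months after the Baseline visit". Footnote c of the Part B Schedule of Activities (1.3.2) repeats it: "This visit is required only for PUPs and MTPs who have less than 40 ED, 6 months after the Baseline visit". In both places the next sentence gives the reason, and it names no exception: "The intent is to have at least one scheduled visit between completion of 20 ED and the expected date of accumulating 50 ED". The text then puts the visit's main purpose as checking well-being and compliance and adjusting the dose.

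Protocol 8.10.2 sets the inhibitor schedule without the condition: "After study treatment is started, PUPs/MTPs must be tested for development of inhibitor to study drug (KOVALTRY) at Visit 3". The list runs on to Visit 7, at "approximately 30 to 40 ED], and Visit 8/Final visit [50 ED]/Early Termination". Section 4.1.2 says "Part B will include 8 study visits" and counts Visit 7 among them. SAP section 3 gives the same count.

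The neighbouring tests are at Visit 6, whose heading begins "Visit 6/ED 20 (20 ED ±1", and at the Final visit. Footnote d allows the Final visit once 50 ED are reached, "but no later than 2 weeks after achieving 50 ED"; the heading of 7.2.8 gives 7 days. Under 6.6.2, routine testing every 3 to 5 ED stops at 20 ED, after which only non-response calls for a test.

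**The concern.** For a child with 40 or more ED at 6 months, 7.2.7 does not require the one visit that its next sentence says every child should have. A site working from 8.10.2 would test that child at 30 to 40 ED. A site working from 7.2.7 could go straight from Visit 6 to the Final visit. The wording of 7.2.7 does not forbid the visit, but nothing schedules it. Dispensing visits in that interval have no inhibitor test specified.

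Inhibitor development is a Part B safety endpoint. Protocol 2.3 calls it the most significant risk of the product, 2.3.1 puts the risk in previously untreated patients at about 30% to 50%, and the mitigation listed there is titer assessment at scheduled visits. At stake is earlier detection of a clinically silent inhibitor, or of a transient one that lasts long enough to be confirmed on a second sample but is gone by 50 ED. SAP 6.4.3 also summarizes inhibitors by time point, and under 7.2.7 a Visit 7 result is assured only for slower-accruing children.

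**Working it through.** **The plan's own figure.** Protocol 9.2.2 gives at least 92% probability of seeing one or more inhibitors among 6 children if the true rate is 35% to 54%. At 35%, 1 − 0.65^6 = 0.925, so the figure reproduces. It is not in dispute, and the Visit 7 rule does not change it.

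**Pace at which Visit 7 stops being required.** Six months = 365.25/2 = 182.6 days = 26.09 weeks. The threshold is 40/26.09 = 1.53 ED per week, averaged from Baseline and counting every ED, including those for treating bleeds.

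**Whether that pace is plausible.** At a constant rate from Baseline, 40 ED in 6 months means 50 ED at 6 × 50/40 = 7.5 months. Section 7.2.8 expects most children to reach 50 ED between 6 and 12 months after prophylaxis starts, so the faster end of the plan's own range can fall under the exemption. At 2 ED per week, 50 ED is reached at week 25, before the 6-month check takes place.

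**Length of the gap.** From Visit 6 at ED 20 to the Final visit is 50 − 20 = 30 ED (29 to 31 with the ±1 window). In weeks it is 30/rate. With Visit 7 at ED 30, 35 or 40, the longest gap is max(V7 − 20, 50 − V7) = 20, 15 or 20 ED.

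| ED per week, constant from Baseline | ED at 6 months (nominal) | Visit 7 required by 7.2.7 | Longest gap now | Longest gap with Visit 7 for all |
|---|---|---|---|---|
| 1 | 26.1 | yes | 15–20 ED, 15–20 weeks | unchanged |
| 1.53 | 40.0 | no | 30 ED, 19.6 weeks | 15–20 ED, 9.8–13.0 weeks |
| 2 | 52.2 | no | 30 ED, 15.0 weeks | 15–20 ED, 7.5–10.0 weeks |
| 3 | 78.3 | no | 30 ED, 10.0 weeks | 15–20 ED, 5.0–6.7 weeks |

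The Final-visit window adds up to 1 week (7.2.8) or 2 weeks (footnote d). One window combination, Visit 6 at ED 19 and Visit 7 at ED 40, gives 21 ED after the change.

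**Why no start-date bound can be given.** Suppose prophylaxis starts d weeks after Baseline at r ED per week, after k on-demand ED. The child is exempt if k + r(26.09 − d) ≥ 40, that is, d ≤ 26.09 − (40 − k)/r. At r = 2:
- k = 0 gives d ≤ 6.1 weeks.
- k = 3 gives d ≤ 7.6 weeks.
- k = 9 gives d ≤ 10.6 weeks.
- k = 12 gives d ≤ 12.1 weeks.

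Section 6.6.2 limits the on-demand phase to 2 to 3 bleeds, not to a number of ED. Table 10–3 gives 3 to 4 days or more of treatment for a moderate bleed, so three such bleeds could use 9 to 12 ED. Breakthrough bleeds after prophylaxis starts add more. Even a weekly-dosed child, with about 26 prophylaxis ED at 6 months, would be exempt with 40 − 26 = 14 further bleed-treatment ED.

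**The case against.** The best defence is that the condition is a calendar safeguard. Well-being, compliance and weight-based dosing need checking as time passes, so the visit is aimed at slow accruers. The table gives this some support: an exempt child's gap of 10 to 20 weeks lies within or below the 15 to 20 weeks of a weekly-dosed child who attends Visit 7. That stands for calendar time. But the documents do not state this rationale, the intent sentence is framed in ED, and in ED the gap is about 30 against 15 to 20.

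Second, 8.10.2 may mean a test at Visit 7 if that visit is held. SoA footnote o, which asks for a test at every visit after treatment starts, fits that reading, and protocol section 7 makes adherence to the SoA essential. A reader might infer a flat contradiction with 8.10.2. The texts support only inconsistent wording. The if-held reading still leaves the intent unmet for faster accruers.

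Third, a reader might infer that these children go untested or that the inhibitor endpoint is lost. Neither follows. Non-response testing (6.6.2), unscheduled visits, calls about every 2 weeks and the 50 ED or early-termination test all remain, so a persistent inhibitor would still be found. The documents do not say what share of inhibitors arise after ED 20.

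Finally, it is tempting to fix a latest prophylaxis start date for exemption, or to say that a weekly-dosed child always gets Visit 7. Bleed-treatment ED rule out both statements.

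**Conclusion.** The point holds in a limited form. Where 7.2.7 is followed, a Part B child with 40 or more ED at 6 months after Baseline has no scheduled inhibitor test for about 30 ED. The stated intent of Visit 7 is unmet for that child only; slower accruers do get the visit. The week figures assume a constant pace from Baseline, while the ED figures need only the visit windows. The number of children affected, out of about 6, cannot be known from the documents and may be zero. The consequence is possible delay in finding a silent inhibitor, a possible missed transient one, and Visit 7 data assured only for slower accruers. The change should be made because it is cheap and concerns the product's main risk. The trial's validity does not depend on it.

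**What to change.** Delete the condition on ED at 6 months from 7.2.7 and from SoA footnote c. Require Visit 7, with its inhibitor test, for all Part B participants at 30 to 40 ED, ideally near ED 35. The intent sentence, 4.1.2, 8.10.2 and the SAP can stay as they are.

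The cost is a protocol amendment with IRB/IEC approval (10.1.1) and, if the consent form changes, re-consent of current participants (10.1.2). Faster-accruing children would have one more visit and one small blood draw, to be kept within the Table 10–1 volume guide.

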### 7.2.8 Final Visit/50 ED (+7 Days)/Early Termination

This visit will take place after 50 ED with study intervention are accumulated in participants who do not develop high titer FVIII inhibitor, or in the case of early termination. It is

expected that 50 ED will be achieved for most participants between 6 and 12 months after the start of prophylactic treatment.

The following procedures and assessments will be performed:

- Height/length and weight
- Physical examination
- Vital signs (see Section [8.2](#) for details)
- Concomitant medication review
- Review of EPD entries and bleeding history
- Blood sampling for laboratory tests
  - FVIII inhibitor assessment (Section [8.10](#))
  - FVIII:C trough level ( $\geq$ 48 hours after the last FVIII treatment)
- In-hospital administration of study intervention
- Blood sampling after administration of study intervention (Section [7.3.2](#)):
  - Incremental recovery (15 to 30 minutes post infusion)
- AE review
- Return of EPD
- Return of used and unused study intervention for final study drug accountability

### **7.2.9 Follow-Up Call (2 Weeks $\pm$ 7 Days After the Final Visit)**

In this telephone contact, each participant's parent/caregiver will be asked about any new AEs and changes in concomitant medication, including FVIII products, since the last study visit.

## **7.3 Efficacy Assessments**

The primary efficacy variable in Part A is the ABR of all bleeding episodes during prophylaxis. The ABR of all bleeding episodes within 48 hours of a previous prophylaxis infusion is the primary efficacy variable in Part B. The ABR of all bleeding episodes during prophylaxis in Part B and the ABR of all bleeding episodes within 48 hours of a previous prophylaxis infusion in Part A will be assessed as secondary efficacy parameters.

Additionally, the ABR for the following efficacy variables will be summarized for both Part A and Part B:

- Treated bleeding episodes
- Joint bleeding episodes
- Joint bleeding episodes within 48h of previous prophylaxis infusion
- Target joint bleeding episodes
- Spontaneous bleeding episodes
- Spontaneous bleeding episodes within 48h of previous prophylaxis infusion
- Spontaneous joint bleeding episodes
- Trauma bleeding episodes
- Trauma bleeding episodes within 48h of previous prophylaxis infusion

Other efficacy variables include:

- Minor surgery bleeding control
- Participants'/parents'/physician's (in case of surgery) assessment of the response to treatment of bleeding episodes (excellent, good, moderate, or poor)
- The number of infusions required to treat a bleeding episode
- Factor VIII usage (expressed as number of infusions and IU/kg per year, as well as IU/kg per event)
- Extent of exposure in terms of exposure days (EDs)
- Type, location, and severity of bleeding episodes
- Reason for each infusion
- Incremental recovery

### 7.3.1 Treatment Logs/Bleeding Verification

Treatment logs are commonly used for hemophilia participants for documentation of their home treatment. Home treatment and bleeding information are the key variables for evaluation of efficacy. Study specific treatment logs will be provided in national language. The preferred system for this study will be EPD devices since they are interactive, allow for real time data transmission, record-stamp date and time of fulfillment, and facilitate the clarification of data with the site and the data cleaning process. Participants will be provided with EPDs for the entire study. At the Screening visit, participants/caregivers will be trained in the use of the device. These logs will be used to collect the treatment data and bleeding episodes by the participants, and the data will be verified for accuracy and completion by the investigator or delegate during regularly scheduled interactions with the participant. Thus, the EPD will be considered the source for these data.

#### Infusion of KOVALTRY

For each self-administered infusion of KOVALTRY, information must be recorded on the EPD as follows:

- a. Date and time
- b. Individual vial number (bar code scan from vial label or manual entry) and units administered
- c. Reason for treatment:
  - Prophylaxis
  - Unscheduled prophylaxis (e.g., for physical activities, suspected or non-evident bleeding following identified trauma)
  - Spontaneous bleeding first treatment
  - Trauma bleeding first treatment
  - Follow-up treatment
  - Surgery
  - ITI (only applicable to participants who develop high-titer inhibitor and received ITI)

Infusions of KOVALTRY as part of protocol mandated visits and procedures (e.g., for recovery and PK) will be recorded on the respective CRF pages.

### Bleeding Episode

All bleeding episodes (regardless if treated or not, or treated at home or under medical supervision) as well as any potential treatment with other hemophilia drugs will be recorded in the EPD:

- a. Date and time of onset
- b. Type of bleeding (spontaneous, trauma, joint, muscle, skin/mucosal, internal, other)
- c. Location
- d. Intensity (mild, moderate, severe)
- e. Treated [yes/no]:  
If “yes”:      Date and time  
                    Product used: KOVALTRY or other  
                    Doses

If KOVALTRY is used for the treatment of a bleeding episode, the response to treatment (excellent, good, moderate, poor, too early to tell) must to be recorded. If “too early to tell” is entered, the participant will be queried for a response the next time the device is used.

For guidance to the participant or their caregiver, the following definitions for response to treatment are suggested. Individual participant responses may vary.

- **Excellent:** Abrupt pain relief and/or improvement in signs of bleeding with no additional infusion administered
- **Good:** Definite pain relief and/or improvement in signs of bleeding, but possibly requiring more than one infusion for complete resolution
- **Moderate:** Probable or slight improvement, with at least one additional infusion for complete resolution
- **Poor (or None):** No improvement or condition worsens

The following additional guidance should be used for clarification of whether information should be recorded in the EPDs or in the CRFs:

- Information on study treatment administration must be captured in either the CRFs or in the EPDs, but not both. Information should not be duplicated.
- All use of study treatment outside the hospital/clinic should be recorded in the EPD.
- Use of study treatment in the hospital/clinic as defined in the protocol (e.g., at protocol-defined visits, for PK or recovery) should be recorded in the CRFs.
  - In the extremely unlikely event that an infusion at a protocol-defined visit is given for a bleeding, the information should be recorded in the EPD rather than the CRFs, since additional information needs to be collected for bleeding that is not collected in CRFs but only in the EPD.
  - Regular prophylaxis infusions that are not defined in the protocol as being administered in the hospital/clinic at a specific visit should be recorded in the EPD regardless of whether they are administered in the hospital/clinic

(e.g., infusion information for a participant whose infusion would have been given at home but had to be given in the hospital because of venous access should be recorded in the EPD).

